5.2. Aldesleukin (Interleukin-2) Administration

Aldesleukin (Interleukin-2, IL-2) will be administered on an inpatient basis. Reported adverse events and potential risks for aldesleukin are described in Section 7.

- Patients will receive a total of 6 cycles (1 cycle = 5 days) of IL-2 as described in section 5.1. A cycle of IL-2 may be delayed for up to 2 weeks in case of unresolved toxicity.
- Aldesleukin will be administered at 600,000 IU/kg IV bolus q 8 hours during

days 1-5 of each cycle (maximum 14 doses per 5 day cycle).

- As all institutions participating in this protocol have established and experienced high dose interleukin-2 programs, the administration of aldesleukin (at the protocol's specified dose and frequency) and the dose delay/discontinuation criteria during a cycle of IL-2 will follow the institutional standard of care guidelines. Useful guides are provided by:
 - Schwartzentruber DJ. J Immunother. 2001 Jul-Aug;24(4):287-93[20].
 - Janice P Dutcher, Douglas J Schwartzentruber, Howard L Kaufman, Sanjiv S Agarwala, Ahmad A Tarhini, James N Lowder and Michael B Atkins. High Dose Interleukin-2 (Aldesleukin) - Expert Consensus on Best Management Practices—2014. Journal for Immunotherapy of Cancer 2014, 2:26 (16 September 2014).

5.3. General Concomitant Medication and Supportive Care Guidelines

Concomitant medications should be kept to a minimum during the study. However, if these are considered necessary for the patient's welfare and are unlikely to interfere with the investigational products, they may be given at the discretion of the investigator and recorded in the CRF.

5.4. Duration of Therapy

In the absence of treatment delays due to adverse events, treatment may continue for per study protocol until one of the following criteria applies:

- X Disease progression,
- X Intercurrent illness that prevents further administration of treatment,
- X Unacceptable adverse events(s),
- X Patient decides to withdraw from the study, or
- X General or specific changes in the patient's condition render the patient unacceptable for further treatment in the judgment of the investigator.
- X Subject non-compliance if deemed severe enough to impact the quality of the data collected. Such cases must be discussed between the local physician investigator and study chair.

5.5. Duration of Follow Up

Patients will be followed for 5 years after removal from study or until death, whichever occurs first. Patients removed from study for unacceptable adverse events will be followed until resolution or stabilization of the adverse event. The frequency and the type of evaluations during this follow up period will follow the Study Calendar. For patients who complete the study procedures wish not to have long term follow up with a study investigator, they can be followed by their treating physician of choice and also following local standard of care practices. Data on disease progression and survival for these patients during long term follow up will be collected on all patients every 3-6 months.

6. ADVERSE EVENTS: LIST AND REPORTING REQUIREMENTS

Adverse event (AE) monitoring and reporting is a routine part of every clinical trial. The following list of AEs (Section 6.1) and the characteristics of an observed AE (Section 6.2) will determine whether the event requires expedited reporting **in addition** to routine reporting.

6.1. Interleukin-2 Adverse Event Summary List

The following AE list was adapted from the Comprehensive Adverse Event and Potential Risks list (CAEPR) for IL2 and provides a single list of reported and/or potential adverse events (AE) associated with an agent using a uniform presentation of events by body system.

Adverse Events with Possible Relationship to Interleukin-2 (CTCAE 4.0 Term)	
BLOOD AND LYMPHATIC SYSTEM DISORDERS	
	Anemia
CARDIAC DISORDERS	
	Conduction disorder
	Left ventricular systolic dysfunction
	Myocardial infarction
	Myocarditis
	Palpitations
	Sinus tachycardia
	Supraventricular tachycardia
	Ventricular arrhythmia
EAR AND LABYRINTH DISORDERS	
	Hearing impaired

EYE DISORDERS	
	Blurred vision
GASTROINTESTINAL DISORDERS	
	Abdominal pain
	Diarrhea
	Dry mouth
	Gastrointestinal disorders - Other (Perforation, GI – Select)
	Gastrointestinal disorders - Other (small bowel fistula)
	Mucositis oral
	Nausea
	Vomiting
GENERAL DISORDERS AND ADMINISTRATION SITE CONDITIONS	
	Chills
	Edema limbs
	Fatigue
	Fever
IMMUNE SYSTEM DISORDERS	
	Allergic reaction
	Autoimmune disorder
INFECTIONS AND INFESTATIONS	
	Infections and Infestations – Other (Infection – Select)
INVESTIGATIONS	
	Activated partial thromboplastin time prolonged
	Alanine aminotransferase increased
	Alkaline phosphatase increased
	Aspartate aminotransferase increased
	Blood bilirubin increased
	Creatinine increased
	GGT increased
	INR increased
	Lymphocyte count decreased
	Platelet count decreased
	Weight gain
	White blood cell decreased
METABOLISM AND NUTRITION DISORDERS	
	Acidosis

	Anorexia
	Hyperuricemia
	Hypocalcemia
	Hypoglycemia
	Hypomagnesemia
	Hyponatremia
	Hypophosphatemia
MUSCULOSKELETAL AND CONNECTIVE TISSUE DISORDERS	
	Arthralgia
	Myalgia
	Myositis
NERVOUS SYSTEM DISORDERS	
	Depressed level of consciousness
	Dizziness
	Headache
	Memory impairment
	Nervous system disorders - Other (sleep disturbances)
	Peripheral sensory neuropathy
	Seizure
PSYCHIATRIC DISORDERS	
	Anxiety
	Confusion
	Personality change
	Psychosis
RENAL AND URINARY DISORDERS	
	Acute kidney injury
RESPIRATORY, THORACIC AND MEDIASTINAL DISORDERS	
	Adult respiratory distress syndrome
	Allergic rhinitis
	Apnea
	Cough
	Dyspnea
SKIN AND SUBCUTANEOUS TISSUE DISORDERS	
	Alopecia
	Pruritus
	Rash maculo-papular
VASCULAR DISORDERS	
	Capillary leak syndrome

	Hypotension
	Peripheral ischemia
	Thromboembolic event
	Vascular disorders - Other (vasodilation)

Also reported on interleukin-2 trials but with the relationship to interleukin-2 still undetermined:

CARDIAC DISORDERS - Mobitz type I; Pericardial effusion

EYE DISORDERS - Eye disorders - Other (mydriasis)

GASTROINTESTINAL DISORDERS - Gastrointestinal disorders – Other (Hemorrhage, GI – Select); Pancreatitis

GENERAL DISORDERS AND ADMINISTRATION SITE CONDITIONS - General disorders and administration site conditions - Other (phospholipid syndrome); Hypothermia; Multi-organ failure

INFECTIONS AND INFESTATIONS – Infections and infestations – Other (Infection (documented clinically or microbiologically with Grade 3 or 4 neutrophils [ANC <1.0 x 10⁹/L]) – Select)

MUSCULOSKELETAL AND CONNECTIVE TISSUE DISORDERS - Soft tissue necrosis lower limb

NERVOUS SYSTEM DISORDERS - Encephalopathy; Syncope

PSYCHIATRIC DISORDERS - Agitation

RENAL AND URINARY DISORDERS - Renal and urinary disorders - Other (acute tubular necrosis)

RESPIRATORY, THORACIC AND MEDIASTINAL DISORDERS - Bronchopulmonary hemorrhage; Bronchospasm; Hypoxia; Pneumothorax; Pulmonary edema

VASCULAR DISORDERS – Phlebitis, splenic infarction (in a patient with a history of thrombocytosis treated with the combination of IL2 and aflibercept).

Note: Interleukin-2 in combination with other agents could cause an exacerbation of any adverse event currently known to be caused by the other agent, or the combination may result in events never previously associated with either agent.

6.2. Adverse Event Characteristics

- **CTCAE term (AE description) and grade:** The descriptions and grading scales found in the revised NCI Common Terminology Criteria for Adverse Events (CTCAE) version 4.0 will be utilized for AE reporting. All appropriate treatment areas should have access to a copy of the CTCAE version 4.0.
- **‘Expectedness’:** AEs can be ‘Unexpected’ or ‘Expected’ for expedited reporting purposes only. ‘Expected’ AEs are those found in Section 6.1 above or in the Aldesleukin package insert as per the standard of care.

- **Attribution** of the AE:
 - Definite – The AE *is clearly related* to the study treatment.
 - Probable – The AE *is likely related* to the study treatment.
 - Possible – The AE *may be related* to the study treatment.
 - Unlikely – The AE *is doubtfully related* to the study treatment.
 - Unrelated – The AE *is clearly NOT related* to the study treatment.

6.3. Expedited Adverse Event Reporting

6.3.1. Expedited Reporting Guidelines – Reporting Requirements for Adverse Events that occur within **30 Days** of the Last Dose of IL-2 on this trial will adopt the following guidelines:

Phase 2 and 3 Trials									
	Grade 1	Grade 2	Grade 2	Grade 3 and 4		Grade 3 and 4		Grades 5	Grades 5
	Unexpected and Expected	Unexpected	Expected	Unexpected with Hospitalization	Unexpected without Hospitalization	Expected with Hospitalization	Expected without Hospitalization	Unexpected	Expected
Unrelated Unlikely	Not Required	Not Required	Not Required	Not Required	Not Required	Not Required	Not Required	10 Calendar Days	10 Calendar Days
Possible Probable Definite	Not Required	Not Required	Not Required	10 Calendar Days	10 Calendar Days	Not Required	Not Required	24-Hour; 5 Calendar Days	10 Calendar Days

Note: All deaths on study require both routine and expedited reporting regardless of causality. Attribution to treatment or other cause must be provided.

- Expedited AE reporting timelines defined:
 - “24 hours; 5 calendar days” – The investigator must initially report the AE within 24 hours of learning of the event followed by a complete report within 5 calendar days of the initial 24-hour report.
 - “10 calendar days” - A complete report on the AE must be submitted within 10 calendar days of the investigator learning of the event.

6.3.2 Expedited Reporting Procedure

If the criteria for expedited reporting are met, the Coordinating Center and the local institutional review board (per institutional reporting requirements) will be notified using the departmental SAE form.

All events meeting the criteria for expedited reporting should be recorded on the departmental SAE form and submitted to:

1. Study Chair: [contact]
2. Study Chair Liaison: [contact]
3. Coordinating Center: [contact] and [contact]
4. Local Institutional Review Board per institutional reporting requirements

In addition to completing appropriate patient demographic and suspect medication information, the report should include as applicable the following information that is available at the time of report within the Narrative (Section C) on the departmental SAE form:

- CTCAE term(s) and grade(s)
- current status of study drug
- all interventions to address the AE (testing and result, treatment and response)
- hospitalization and/or discharge dates
- event relationship to study drug

Follow-up reports:

Additional information may be added to a previously submitted report by adding to the original departmental SAE form and submitting it as follow-up.

6.4 Data and Safety Monitoring Plan

Investigator/Sub-investigators, regulatory, CRS management, clinical research coordinators, clinical research associates, data managers, and clinic staff meet monthly in disease center Data Safety Monitoring Boards (DSMB) to review and discuss study data to include, but not limited to, the following:

- serious adverse events
- subject safety issues
- recruitment issues
- accrual
- protocol deviations
- unanticipated problems
- breaches of confidentiality

All toxicities encountered during the study will be evaluated on an ongoing basis according to the NCI Common Toxicity Criteria version 4.0. All study treatment associated adverse events that are serious, at least possibly related and unexpected will be reported to the IRB. Any modifications necessary to ensure subject safety and decisions to continue, or close the trial to accrual are also discussed during these meetings. If any literature becomes available which changes the risk/benefit ratio or suggests that conducting the trial is no longer ethical, the IRB will be notified in the form of an Unanticipated Problem submission and the study may be terminated.

All study data reviewed and discussed during these meetings will be kept confidential. Any breach in subject confidentiality will be reported to the IRB in the form of an Unanticipated Problem submission. The summaries of these meetings are forwarded to the UPCI DSMC which also meets

monthly following a designated format.

For all research protocols, there will be a commitment to comply with the IRB's policies for reporting unanticipated problems involving risk to subjects or others (including adverse events). DSMC progress reports, to include a summary of all serious adverse events and modifications, and approval will be submitted to the IRB at the time of renewal.

Protocols with subjects in long-term (survival) follow-up or protocols in data analysis only, will be reviewed twice a year rather than monthly by the disease center DSMB.

Both the UPCI DSMC as well as the individual disease center DSMB have the authority to suspend accrual or further investigate treatment on any trial based on information discussed at these meetings.

All records related to this research study will be stored in a locked environment. Only the researchers affiliated with the research study and their staff will have access to the research records.

7. PHARMACEUTICAL INFORMATION

A list of the adverse events and potential risks associated with the commercial agent administered in this study can be found in Section 6.1.

7.1. Commercial Agents

7.1.1. Interleukin-2

Other Names: Aldesleukin, IL-2, rIL-2, T-cell growth factor

Classification: Biological response modifier

Mode of Action: Endogenous substance secreted by OK-T4 cells and lymphocytes. Enhances primary and secondary cytotoxic T-cell responses, causes T-cell mitogenesis and proliferation, and enhances non-killer cell activity.

Storage and Stability: Intact vials are stored in the refrigerator (2-8°C) with protection from light. Each vial bears an expiration date.

Reconstituted IL-2 should be further diluted with 5% Dextrose, USP. It is not to be mixed with saline-containing solutions. Reconstituted IL-2 may be diluted as necessary in volumes of 50 ml to 500 ml with 5% Dextrose, USP plus 0.1% Albumin Human, USP. When diluting, the Albumin Human, USP should be added to the 5% Dextrose Injection, USP prior to the addition of the IL-2. When diluted for IV administration in 5% Dextrose Injection, USP, a plastic bag (e.g., Viaflex, manufactured by Travenol Laboratories, Inc.) containing 0.1% Albumin Human. IL-2 is chemically stable for 48 hours at refrigerated and room temperatures, 2-30°C.

Dose Specifics: Interleukin-2 600,000 MIU/kg/dose or 720,000 MIU/kg/dose over 15 minute IV infusion every 8 hours on Days 1-5 of each cycle for a maximum of 14 doses. For the purpose of this study, interleukin-2 will be given at 600,000 MIU/kg.

Preparation: Aseptically inject 1.2 ml of sterile water for injection into the vial to dissolve the lyophilized cake. Since contents of the vial are under vacuum, the diluent should be directed against the sides of the vial to avoid excess foaming. Remove flip-off plastic cap and swab the target area of the stopper with antiseptic.

Administration: For sterility considerations, the reconstituted IL-2 should be administered immediately or held at 2-8°C for up to 12 hours in 1.2 ml of sterile water for injection, and is stable for at least 24 hours at room temperature.

Incompatibilities: Incompatible with normal saline (results in a precipitate). It should not be mixed with anything except D5W and sterile water.

Availability: IL-2 is a FDA approved therapy for melanoma and is commercially available.

Toxicity: See section 6.1.

For more information please refer to the drug’s package insert.

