2.2. High Dose Interleukin-2

IL-2 plays a central role in immune regulation as it affects the survival of key cells of the immune system that are responsible for the antitumor cytotoxicity of T-lymphocytes and natural-killer (NK) cells, and it has a cofactor role in the activation of B cells and macrophages [5]. The administration of IL-2 at high bolus IV doses once every eight hours was a regimen developed by the National Cancer Institute (NCI) based on animal models indicating that antitumor activity with this agent was dose-dependent [6-8]. Initial studies with HDB IL-2 utilized doses of 600,000-720,000 units/kg every 8 hours from days 1-5 (cycle 1) and days 15-19 (cycle 2) with a maximum of 14 doses per cycle or 28 doses per course (1 course = 2 cycles). Responding or stable patients were offered a second course of therapy 8-12 weeks later. IL-2 was administered either as a single agent or in combination with immunologically active cells, so-called adoptive immunotherapy. The latter technique utilized two types of immune cells: the lymphokine-activated-killer (LAK) cells and the tumor infiltrating lymphocytes (TIL). Eight clinical trials conducted between 1985 and 1993 and using the HDB IL-2 regimen described above, with or without LAK cells, were reviewed in a retrospective analysis. These trials had an enrollment of 270 patients with advanced metastatic melanoma [7-11]. In those studies that involved the concurrent administration of LAK cells, these cells were obtained using leukapheresis from patients during the rebound lymphocytosis that occurs following treatment and cessation of bolus IL-2 (days 8 to 12). LAK cells were then cultured in IL-2 for 3 to 4 days. These generated LAK cells were reinfused with IL-2 during the second cycle of IL-2 administration. The retrospective analysis of these trials with a follow-up through December 1998 along with a more recent update demonstrated an objective response rate of 16% with durable responses in 4% of patients [2, 10-12]. The median response duration was 8.9 months (range 4 to 106+ months). Twenty eight percent of the responding patients, including 59% of those patients who had achieved a complete response, have remained progression free at a median follow-up of 62 months. Furthermore, no patient who had responses longer than 30 months has relapsed, suggesting the possibility that these patients may be “cured”. The frequency of the responses was similar in patients with visceral metastases and/or large tumor burdens, but the responses were less in patients with poor performance status or those who had received prior systemic therapy. Based on these data, HDB IL-2 received approval by the US-FDA for the treatment of metastatic melanoma [11-13]. In addition to being logistically challenging, randomized studies have not shown superiority for IL-2 administered with LAK cells versus therapy with HD IL-2 alone [12-14]. Furthermore, a randomized phase III trial of CD8+ TIL given in combination with rIL-2 in metastatic renal cell carcinoma has been negative [13-15]. We have previously shown that HD IL2 is an active therapy for patients who progress on biochemotherapy; this observation has implications regarding the importance of dose intensity for IL-2 therapy [16]. Continuous infusion of IL-2 at intermediate dosage is a critical component of biochemotherapy regimens and it was previously unknown whether patients treated with biochemotherapy and failing to obtain response, or responding and then demonstrating progression, are capable of subsequently responding and benefiting clinically from the HD IL2 regimen.

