5. TREATMENT PLAN

5.1. Overall Treatment Plan

This is a phase II study of high dose bolus interleukin-2 (HD IL2) in patients with advanced inoperable stage III or stage IV melanoma who have prior anti-PD1 immunotherapy.

Definitions:

1. A cycle of IL-2: eligible patients receive HD IL2 at 600,000 IU/kg IV every 8 hours for up to 14 doses. This constitutes one cycle of IL2.

2. Each course consists of 2 cycles of HD IL2 as follows: high-dose IL2 at 600,000 IU/kg is given IV every 8 hours for up to 14 doses (one cycle), followed by a rest period of 1-2 weeks and readmission for a second HD IL2 cycle for up to 14 doses (2nd cycle).
3. Based on the occurrence of treatment-related toxicities and requirements for dose adjustments or delays, a patient may or may not receive the full planned treatment, but response assessment will continue to be carried out at the end of each course.

The planned treatment consists of 3 courses (6 cycles) of HD IL-2. Response assessment will occur at the end of each course of therapy and patients without evidence of disease progression (RECIST v.1.1) or limiting toxicities will be offered additional courses of treatment of HD IL2 for a maximum of 3 courses.

	Course of HD IL2*							
	Wk 1	Wk 2	Wk 3	Wk 4	Wk 5	Wk 6	Wk 7	Wk 8
HD IL-2 600,000 U/kg/dose IV Q8h x 5 days (max 14 doses)	X		X					
Response Assessment								X

*Local variations are allowed as per local site standard practice, patient recovery from adverse events and scheduling requirements.

Patients will receive HD IL-2 following the institutional standard of care guidelines. Patients will receive a maximum of 3 courses (6 cycles; 1 course of IL2 = 2 cycles of IL2). Response assessment will be carried out at the end of each course. In the absence of disease progression by RECIST v.1.1, patients will be offered additional courses of therapy for a maximum of 3 courses (6 cycles).

Research biospecimens will be collected at the multiple time points as noted in section 8.1.1.

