9. STUDY CALENDAR

Study investigators should follow the local institutional standard of care guidelines for safety monitoring and safety laboratory testing. Baseline evaluations are to be conducted within 2 weeks prior to administration of HD IL2, unless indicated otherwise, elsewhere in the protocol. Scans and X-rays must be done not more than 28 days prior to the start of HD IL2. In the event that the patient's condition is deteriorating, laboratory evaluations should be repeated within 48 hours prior to initiation of the next cycle of IL2.

Course 1	Pre-Study	Wk 1	Wk 2	Wk 3	Wk 4	Wk 5	Wk 6	Wk 7	Wk 8	Off Study ^f
Interleukin-2 ^a		X		X						
Informed consent	X									
Demographics	X									
Medical history	X									
Concurrent meds	X	X-----X								
Physical exam	X	X		X						X
Vital signs	X	X		X						
Height	X									
Weight	X	X		X						
Performance status	X	X		X						X
CBC w/diff, plts Urinalysis	X	X		X						X
Serum chemistry	X	X		X						X
PT/INR	X									
Cardiac stress test ^b	X									
PFTs ^c	X									
Adverse event evaluation		X-----X								
Tumor measurements	X								X	X
Radiologic evaluation ^d	X								X	X
B-HCG ^e	X									
Research Biospecimen	See Section 8.1.1									

- a: IL-2: 600,000 U/kg/dose IV Q8h x 5 days (max 14 doses) starting on day 1 of weeks 1 and 3. An IL-2 cycle may be delayed until the resolution of limiting toxicities.
- b: Patients who are over 40 years old or have had previous myocardial infarction greater than 6 months prior to study entry or have significant cardiac family history (CAD or serious arrhythmias) will be required to have a negative or low probability cardiac stress test (thallium stress test, stress MUGA or exercise stress test) for cardiac ischemia within 8 weeks prior to registration. Patients who are not required to have a cardiac stress test should have an electrocardiogram at baseline to be reviewed by the treating physician investigator. Patients who undergo echocardiography as part of their cardiac stress test are not required to have a separate baseline echocardiogram.
- c: Pulmonary function tests (PFTs) are required for patients over 50 years old or with significant pulmonary or smoking history. PFTs may be done up to 4 weeks prior to registration.
- d: Radiologic evaluation should include MRI or contrast CT of the brain at baseline and may be repeated at later time points as clinically indicated.
- e: Serum pregnancy test (women of childbearing potential).

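### Section 7.1.1 states the study dose in an undefined unit, MIU/kg, which conflicts with the IU/kg and U/kg used for the same number elsewhere in the protocol

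*Combined protocol and SAP*

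**What the plan says.** The protocol states the HD IL-2 dose in several places.

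- **Section 5.1**, defining a cycle: "eligible patients receive HD IL2 at 600,000 IU/kg IV every 8 hours for up to 14 doses". The schema definitions give the same dose in the same unit.
- **Section 5.2**, on administration: "Aldesleukin will be administered at 600,000 IU/kg IV bolus q 8 hours".
- **Section 9**, calendar footnote a: "IL-2: 600,000 U/kg/dose IV Q8h x 5 days (max 14 doses) starting on day 1 of weeks 1 and 3". The schema table and the table in 5.1 use the same unit as this footnote.
- **Section 7.1.1**, Dose Specifics, lists two dose levels: "Interleukin-2 600,000 MIU/kg/dose or 720,000 MIU/kg/dose over 15 minute IV infusion every 8 hours on Days 1-5 of each cycle". It then selects one for this trial: "For the purpose of this study, interleukin-2 will be given at 600,000 MIU/kg".
- **Section 2.2**, background on the early trials: "utilized doses of 600,000-720,000 units/kg every 8 hours".

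The abbreviations list does not include MIU. No section explains the change of unit or ranks one dose statement above another.

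**The concern.** The numeral is 600,000 in every statement of the study dose, but in 7.1.1 the unit carries an extra letter that would normally be read as a multiplier. If it is one, 7.1.1 and the treatment plan prescribe different amounts and cannot both be followed. The sentence is not background: it selects the dose for this study, and it stands beside the reconstitution, dilution, storage and administration instructions.

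The matter is one of patient safety, not statistics. The drug is given to inpatients, and the protocol's own adverse event list includes capillary leak syndrome, myocardial infarction and adult respiratory distress syndrome. A dose instruction for such an agent should be open to only one reading.

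**Working it through.** The documents contain no derived figure to reproduce. The check is a comparison of the dose statements, followed by unit arithmetic.

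**Step 1. The statements side by side.**

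| Place | Number | Unit as printed |
|---|---|---|
| Schema definitions | 600,000 | IU/kg |
| Schema table | 600,000 | U/kg/dose |
| 2.2 (historical range) | 600,000 to 720,000 | units/kg |
| 5.1, definitions | 600,000 | IU/kg |
| 5.1, table | 600,000 | U/kg/dose |
| 5.2 | 600,000 | IU/kg |
| 7.1.1, listed levels | 600,000 and 720,000 | MIU/kg/dose (printed twice) |
| 7.1.1, study dose | 600,000 | MIU/kg |
| 9, footnote a | 600,000 | U/kg/dose |

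MIU occurs three times, all within one paragraph, so a stray character from text extraction is unlikely.

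**Step 2. Which differences carry a multiplier.** U/kg, units/kg and IU/kg have no prefix, so the text implies no numerical factor between them. That is a lesser labelling inconsistency. The only difference that can change the amount is the M in 7.1.1.

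**Step 3. Size under each reading of M.** The documents do not define M, so each line below is an assumption. Each also assumes that the IU after the prefix is the IU of 5.1 and 5.2.

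Ratio = (600,000 × M) / 600,000 = M

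- M = million: 600,000 × 10^6 = 6 × 10^11 IU/kg; divided by 6 × 10^5, the ratio is 10^6.
- M = thousand: 600,000 × 10^3 = 6 × 10^8 IU/kg; the ratio is 10^3.
- M = milli: 600,000 × 10^-3 = 600 IU/kg; the ratio is 10^-3.

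The sections agree only if M = 1, that is, if the letter means nothing. None of the three multiplier readings gives that.

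**Step 4. Does any other text settle it?** There is no definition and no order of precedence. Section 5.2 leaves administration and the delay and discontinuation criteria to institutional guidelines, but ties administration to the dose and frequency that the protocol sets. Section 7.1.1 sends the reader to the package insert for further information, without saying that the insert overrides the dose printed there. Neither removes the conflict.

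**The case against.** The strongest case on the other side is that this is a slip in a label and that no site would act on it. Much of that stands.

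- The numerals match throughout. The pair 600,000 and 720,000 in 7.1.1 is the same pair that Section 2.2 gives in units/kg. This points to one intended dose with a wrong label rather than to two intended doses, although the documents do not say so.
- Section 5.2 states that all participating institutions have established, experienced high-dose IL-2 programs, and it cites two management guides. The agent is commercially available and 7.1.1 refers to its package insert. All this makes literal use of the label less likely.
- The dose is also set in the schema, 5.1, 5.2 and the calendar, none of which uses MIU. The sentence in 7.1.1 is not the only one that fixes it.
- The documents report no dosing error and no confusion at a site.

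What does not stand is the step from unlikely to harmless. Experienced staff are a safeguard against a wrong sentence, but they do not correct it, and 5.2 sends those same staff back to the protocol for the dose.

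A reader might also infer that 7.1.1 is the text from which pharmacies work, so that the error would pass into order sets or a pharmacy manual. The documents do not say who uses which section and mention neither kind of document, so that inference is not supported.

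**Conclusion.** The point holds as an internal inconsistency: Section 7.1.1 is wrong as written against the schema, 5.1, 5.2 and calendar footnote a. No design choice is at issue, and nothing in the sample size, power, stopping rule or analysis depends on it.

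Its size cannot be read from the documents. It is 10^6, 10^3 or 10^-3 according to the meaning assumed for M. A reader might infer that the protocol literally orders a million-fold overdose. The text does not support that, because MIU is undefined and the matching numerals favour a label slip. A reader might also count three conflicting doses, but U/kg against IU/kg carries no multiplier, so the substantive conflict is confined to the prefix in one paragraph.

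It still needs correcting, because it concerns a dose instruction, every multiplier reading leaves the sections apart by orders of magnitude, and no text in the protocol resolves it. Which statement is intended is for the sponsor to confirm.

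**What to change.** The sponsor should confirm the intended dose and unit, then reconcile the schema (definitions and table), Section 5.1 (definitions and table), Section 5.2, Section 7.1.1 (all three occurrences) and calendar footnote a, so that each states one dose in one unit. That unit should be defined once, for example in the abbreviations list, which at present does not cover dose units. This review proposes no dose.

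The cost is a wording correction in the next amendment. No analysis, sample size or trial procedure changes.
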